Among the latest cosmetic trends in the millennial consumer group is *prejuvenation*, a portmanteau combining the words prevention and rejuvenation.⁵ Prejuvenation utilizes minimally-invasive procedures with the intention of maintaining a youthful appearance and ideally delaying visible signs of aging.⁵⁻⁶ This trend highlights the focus of millennials on early maintenance treatments to produce natural-appearing results in order to avoid or delay more invasive procedures down the line. Cosmetic injectables such as neuromodulators and dermal fillers have become the leading products utilized to achieve these results.⁴ Neuromodulating agents have been used cosmetically to reduce the appearance of dynamic rhytids and fine lines while dermal fillers have been utilized to improve volume distribution and ultimately achieve balanced facial contouring.^{7-8,11} By inhibiting muscles from contracting, neuromodulating agents decrease facial movement and in theory may be used preventatively to suspend the development of wrinkles.⁷⁻⁸ A long-term twin study seeking to evaluate the prevention of wrinkles with neuromodulating agents concluded that long-term onabotulinumtoxinA treatment can effectively prevent facial lines present at rest.⁹ This study, although limited by design, suggests that long-term treatment with neuromodulating agents can lead to the prevention of future wrinkles, providing supporting evidence for prejuvenation. An additional study demonstrated similar results with long-term treatment of glabellar rhytids with onabotulinumtoxinA, further supporting the use of neuromodulators for prejuvenation.¹⁰

Given the subjectivity of beauty standards and desired outcomes, patient satisfaction remains paramount in evaluating the success of aesthetic treatments. The HARMONY study utilized patient-reported outcomes as a primary measure for a multimodal facial aesthetic treatment in a cohort of patients aged 37-65.¹² While the HARMONY study's primary outcome measure focused on patient satisfaction of post-procedural facial appearance, several of their secondary outcome measures were reflective of their cohort being comprised of an older-age group: patient's perceived

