- Known hypersensitivity or allergies to any of the components of the administered drugs/devices in the study (e.g., Gram-positive bacterial proteins, lidocaine)
- History of anaphylaxis or multiple severe allergies
- History of a bleeding or coagulation disorder
- Pregnant or breast-feeding
- Current and/or scheduled use of the following medications: immunosuppressants, anticoagulants (e.g., warfarin, heparin, rivaroxaban), antiplatelets (e.g., clopidogrel, ticagrelor, NSAIDs), antibiotics (e.g., aminoglycosides), anticholinergics, muscle relaxants
- Procedures or treatments to the face in the past 14 days (e.g., chemical peel, laser surgery, microdermabrasion)

- Plan to undergo elective cosmetic procedure on the face (e.g., laser surgery, plastic surgery, physician-strength chemical peel) during the study
- Any medical condition(s) that could be compromised by participating in the study

SAMPLE SIZE

20

METHOD FOR SCREENING FOR ELIGIBILITY

At the in-person screening visit, the research team will screen potential study subjects by asking about demographics, medical history pertinent to the eligibility criteria, and prior and concomitant medications. On the case report form titled “Eligibility Checklist,” all inclusion criteria boxes must be marked *yes* and all exclusion criteria boxes must be marked *no* for a potential study subject to be eligible to enroll and participate in the study.

INCLUSION OF VULNERABLE POPULATIONS

Vulnerable populations will not be included in this study.

STATISTICAL CONSIDERATIONS

ANALYSIS PLAN

Statistical analyses will be performed using SAS version 9.4 statistical package (SAS Institute, Cary, NC, USA) or similar. Efficacy analyses will be conducted on the modified intent-to-treat population (mITT). Statistical analysis will be modeled after the HARMONY study.¹² The raw scores of the primary outcome measure (FACE-Q Satisfaction with Facial Appearance Scale) will be transformed by the Rasch measurement method into a 0-to-100 point scale.¹⁴⁻¹⁵ Data will be analyzed using a paired *t*-test. Secondary outcome measures will also be analyzed using paired *t*-tests. Categorical variables will be presented as proportions. Pearson χ^2 tests will be used to compare categorical variables between subgroups. A *p*-value < 0.05 is considered to be statistically significant.

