Subgroup analysis will be performed on participants that have demonstrated significant improvement on outcome measures, as defined by post-treatment scores falling outside the 95% confidence intervals for baseline scores.

Adverse events (AE) will be categorized into general, product-related, or procedure-related AEs. These will be summarized by severity of reported event, timing of reported event, and percentage of participants with each reported event.

SAMPLE SIZE JUSTIFICATION

This is a pilot study that is designed to evaluate differences in satisfaction with facial appearance before and after the study intervention. No power analysis was performed to determine a target sample size.

PROCEDURES AND DATA COLLECTION

All study procedures will take place in [name] Photomedicine Research Clinic, located in Suite C of University Hospital of Brooklyn, or the Clinical and Translational Science Center (CTSC) at SUNY Downstate Medical Center. All study participants must provide written informed consent before any study related procedures are performed. The study will be conducted as outlined in the schedule of assessments (Table 1).

SCREENING

At the screening visit, potential study participants will be asked to provide the following information to be recorded in the case report forms: demographics (date of birth, sex, race, ethnicity); medical history pertinent to the eligibility criteria; prior and concomitant medications. The research team will determine whether potential study participants meet the inclusion and exclusion criteria specified in the "Eligibility Checklist" case report form. Subjects who meet all of the inclusion criteria and none of the exclusion criteria will be eligible for study entry.

FACIAL AESTHETIC TREATMENT

Study participants will undergo an elective, minimally invasive cosmetic procedure involving the administration of botulinum toxin and dermal fillers. All procedures will be performed by [name] (principal investigator), a board-certified dermatologist and cosmetics expert.

DRUG & DEVICE DESCRIPTION

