Efficacy assessments are conducted at baseline (prior to undergoing the facial aesthetic treatment) and at the follow-up study visits scheduled at 2 months after the procedure. Participants will be asked to attend the study visits without facial make-up or to remove any facial make-up prior to the assessments.

SATISFACTION QUESTIONNAIRES - BASELINE

At the baseline visit, participants will be asked to complete several validated questionnaires to evaluate their current level of satisfaction with various facial areas, as well as psychosocial attitudes and perceptions regarding facial aesthetic treatments. The following surveys/questionnaires will be administered prior to the procedure:

- Millennial Facial Aesthetics Survey
- FACE-Q Aging Appraisal
- FACE-Q Patient-Perceived Age VAS
- FACE-Q Expectations
- FACE-Q Satisfaction with Facial Appearance

- FACE-Q Social Function
- FACE-Q Psychological Function
- FACE-Q Appraisal of Lines: Overall
- FACE-Q Appraisal of Lines: Between Eyebrows
- FACE-Q Appraisal of Lines: Forehead
- FACE-Q Appraisal of Lines: Crow's Feet
- FACE-Q Satisfaction with Cheeks
- FACE-Q Appraisal of Lines: Lips *and/or* FACE-Q Satisfaction of Lips (depending on the area treated with filler)

SATISFACTION QUESTIONNAIRES – FOLLOW-UP

The following surveys/questionnaires will be administered at the final study visit:

- FACE-Q Aging Appraisal
- FACE-Q Patient-Perceived Age VAS
- FACE-Q Satisfaction with Facial Appearance
- FACE-Q Satisfaction with Outcome
- FACE-Q Social Function
- FACE-Q Psychological Function
- FACE-Q Appraisal of Lines: Overall
- FACE-Q Appraisal of Lines: Between Eyebrows
- FACE-Q Appraisal of Lines: Forehead
- FACE-Q Appraisal of Lines: Crow's Feet
- FACE-Q Satisfaction with Cheeks
- FACE-Q Appraisal of Lines: Lips *and/or* FACE-Q Satisfaction of Lips (depending on the area treated with filler)
- Exit Questionnaire

PHOTOGRAPHY

Standardized photographs of the face will be taken in 3 views – full frontal, left lateral, and right lateral – with a digital single-lens reflex (DSLR) camera. Additional photographs will be taken using

the VECTRA H2 3D camera (Canfield Scientific, Parsippany, NJ) and VISIA Complexion Analysis System (Canfield Scientific, Parsippany, NJ) for documentation purposes.

CLINICAL EVALUATION

A blinded evaluator will provide a score on the Global Aesthetic Improvement Scale (GAIS) to assess overall cosmetic results based on photographs obtained at the final study visit as compared to baseline.

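### The rule for classing a participant as significantly improved does not name its 95% interval, and on its ordinary reading it ignores the participant's own baseline and marks about a third as improved before treatment

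*Combined protocol and SAP*

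**What the plan says.** The rule is in Statistical Considerations, Analysis Plan. It first says who is selected: "Subgroup analysis will be performed on participants that have demonstrated significant improvement on outcome measures". The criterion is then given in these words: "as defined by post-treatment scores falling outside the 95% confidence intervals for baseline scores". No formula, SD, standard error of measurement (SEM) or reliability is given.

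Three other places bear on how to read it.

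- **Source of the method.** The same section states "Statistical analysis will be modeled after the HARMONY study". The Introduction describes that study's population and outcomes ("The HARMONY study utilized patient-reported outcomes as a primary measure for a multimodal facial aesthetic treatment in a cohort of patients aged 37-65") but not how it classed individuals.
- **Scoring.** "The raw scores of the primary outcome measure (FACE-Q Satisfaction with Facial Appearance Scale) will be transformed by the Rasch measurement method". This is stated for the primary scale only, and no person-level standard error is mentioned.
- **Timing and scales.** Under Efficacy Assessments, "Efficacy assessments are conducted at baseline (prior to undergoing the facial aesthetic treatment) and at the follow-up study visits scheduled at 2 months". Each questionnaire is therefore completed once before treatment. The list mixes satisfaction scales, appraisals of lines and the "FACE-Q Patient-Perceived Age VAS". The instruments are described as validated ("participants will be asked to complete several validated questionnaires to evaluate their current level of satisfaction with various facial areas"), but the protocol does not write out which end of each scale is favourable.

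**The concern.** The rule labels individuals, so it needs an interval suited to individuals. A confidence interval ordinarily describes uncertainty about a mean. It narrows as the sample grows and says little about how far one person's score must move to show real change. If it is used as a cut-off for individuals, everyone is compared with one common limit. A participant who starts beyond that limit counts as improved without changing, or even after falling. One who starts well below it can gain a good deal and not count.

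Two other readings are open: the spread of individual baseline scores, or a measurement-error band around each participant's own baseline. The three use different inputs (cohort standard error, cohort SD, individual SEM), and the plan chooses none. At stake are who enters this subgroup and any count of improvers taken from it. If the interval is chosen after the data are seen, that count could move severalfold.

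**Working it through.** The plan states no flag rate, so there is no figure of its own to reproduce.

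**Inputs from the protocol.** n = 20; one group; one pre-treatment assessment; 95% level. Only the favourable side is counted, because the rule concerns improvement.

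**Assumptions not in the protocol.** Roughly normal scores with equal SD before and after; pre-post correlation r = 0.5 to 0.9; reliability 0.90 where an SEM is needed. Results are in baseline SD units.

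**Reading (a): confidence interval of the cohort's baseline mean.**
- Half-width = t(0.975, 19)/√20 = 2.093/4.472 = 0.468 SD.
- Share beyond it on the favourable side at baseline = 1 − Φ(0.468) = 0.320, or 0.320 × 20 ≈ 6 people. This does not depend on r or on the treatment effect, but it does depend on the shape of the scores.
- With 15 evaluable participants, the half-width is 0.554 SD and the share 0.290.

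Simulation with the baseline mean and SD estimated from each sample of 20:

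| Mean gain | r | Flagged | Of flagged: already outside at baseline | Of flagged: fell from own baseline |
|---|---|---|---|---|
| 0 | 0.5 | 32% | 53% | 26% |
| 0 | 0.7 | 32% | 64% | 31% |
| 0 | 0.9 | 32% | 79% | 39% |
| 0.5 SD | 0.5 | 52% | 46% | 16% |
| 0.5 SD | 0.7 | 52% | 53% | 15% |
| 0.5 SD | 0.9 | 52% | 60% | 9% |

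The rule also misses people. With no mean change and r = 0.5, 52% of those who rose were not flagged.

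Thirteen non-normal shapes were also tried: gamma, exponential and lognormal, each skewed in both directions; uniform; five beta shapes; and t with 4 df. With no mean change, 24-41% were flagged, 24-41% were already outside at baseline, and 22-41% of those flagged had fallen.

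**Reading (b): own baseline ± 1.96 SEM.** SEM = √(1 − 0.90) = 0.316 SD, so the limit is 1.96 × 0.316 = 0.620 SD. The SD of change is √(2(1 − r)).
- If no individual truly changes, r equals the reliability, and the rate is 1 − Φ(1.96/√2) = 8.3%.
- If only the mean is unchanged: r = 0.5, 1 − Φ(0.620/1.000) = 26.8%; r = 0.7, 1 − Φ(0.620/0.775) = 21.2%; r = 0.9, 8.3%.

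This reading uses own change but ignores measurement error in the second score.

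**Reading (c): baseline mean ± 1.96 SD.** With no mean change, about 2-3% are flagged (0-6% over the non-normal shapes). It also ignores own change.

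**Comparator: reliable-change threshold, 1.96 × √2 × SEM** = 1.96 × 1.414 × 0.316 = 0.88 SD.
- If no individual truly changes: 1 − Φ(1.96) = 2.5%.
- If only the mean is unchanged: r = 0.5, 1 − Φ(0.877/1.000) = 19.0%; r = 0.7, 12.9%; r = 0.9, 2.5%.

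The two conditions must be kept apart. When r is below the reliability, some participants really do change although the mean does not. Flags above 8.3% or 2.5% may then be real individual change rather than error.

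**The case against.** The strongest reply is that nothing shows the investigators mean to compare individuals with a confidence interval of the mean. The rule speaks of intervals in the plural and comes shortly after the Rasch scoring, so a band for each person is a natural reading. The plan also points to a model study, where the rule may be fully defined. On that view the defect is only a definition not restated, and the 32% belongs to a reading nobody intends.

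Much of this stands. The intended reading is unknown, and 32% is conditional on reading (a) and near-normal scores. But the plural may simply reflect several outcome measures, Rasch scoring is stated only for the primary scale, and the model study's interval is not in the protocol. Neither clue settles the matter.

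A second reply is that a reliable-change rule is not as strict as 2.5% suggests. That is right. With no mean change it can flag up to 19% under the assumptions used here, so setting 32% against 2.5% would overstate the gain. The case for it is that it judges each person's own change and allows for error in both scores.

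A third reply is that this is a 20-person pilot with no power analysis. That bears on severity, not on whether the rule can be programmed as written.

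**Conclusion.** The point holds and is minor. The interval is not named, and the documents do not settle it. On the ordinary reading the rule does not measure individual improvement: about 32% of participants (24-41% over the non-normal shapes) are on the favourable side before treatment, about the same share is flagged with no mean change, and 26-39% of those flagged have fallen from their own baseline at an assumed r of 0.5 to 0.9. The spread-of-scores reading flags about 2-3% but shares the disregard of own change. The own-baseline SEM reading is workable but lenient: 8.3% if no individual truly changes, and 8-27% with no mean change at an assumed reliability of 0.90.

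A reader might infer that the trial will in fact mislabel a third of its cohort. The documents do not support that, because they do not say that reading (a) will be used. A reader might also infer that the evidence of efficacy is compromised. It is not: the primary and secondary paired t-tests do not use this rule.

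**What to change.** For each scale, define improvement on the participant's own change from baseline, in a stated favourable direction, against a stated individual-change threshold. One option is 1.96 × √2 × SEM with the source of the SEM named, such as published reliability or, for the primary scale, the standard errors from Rasch scoring. With one pre-treatment assessment, a retest SEM cannot be estimated in this cohort; where no SEM can be justified, report the change only. Report improvement and deterioration separately with exact 95% intervals, and treat the subgroup as descriptive, since it is selected on outcome.

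At minimum, one or two sentences should name the interval and the favourable direction. If the rule comes from the model study, restate it in the protocol, and do not use a confidence interval of the cohort mean to classify individuals.

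The cost is a short paragraph and a table of scales, direction and SEM source, with no new data. Some work is needed to source an SEM for the 11 or 12 scales given at both visits. Fewer participants may be counted as improved, and smaller real gains will be missed: the threshold is 0.88 baseline SD at reliability 0.90 and 1.24 at 0.80. The percentage will also be imprecise: 5 of 20, for example, has an exact 95% interval of 9-49%.

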The three types of facial injectables to be used are Botox Cosmetic (onabotulinumtoxinA), Juvéderm Voluma XC (hyaluronic acid gel filler), and Juvéderm Volbella XC (hyaluronic acid gel filler). The U.S. Food and Drug Administration (FDA) classifies Juvéderm Voluma XC and Juvéderm Volbella XC as devices, and Botox Cosmetic as a drug. Botox Cosmetic is an acetylcholine release inhibitor and a neuromuscular blocking agent. Juvéderm Voluma XC and Juvéderm Volbella XC are gel implants consisting of cross-linked hyaluronic acid.

The FDA has approved these treatments for the following indications:

- Botox Cosmetic: injection into muscle to temporarily improve the appearance of frown lines between the eyebrows and crow's feet lines in adults
- Juvéderm Voluma XC: deep (subcutaneous and/or supraperiosteal) injection for cheek augmentation to correct age-related volume deficit in the mid-face in adults
- Juvéderm Volbella XC: injection into the lips for lip augmentation and for correction of perioral lines in adults

DOSAGE AND ADMINISTRATION

The products will be administered by intramuscular injection according to the manufacturer's prescribing information/package insert. The injection sites, treatment areas, and volumes/dosages of each product used will be documented in the appropriate case report form. The lot number and expiration date for each product will also be recorded.

Each participant will receive all three products using standard injection technique during a single procedure:

1. **Botox Cosmetic (onabotulinumtoxinA)**: up to 50 units in the following three anatomic regions

- a. Frontalis (forehead): up to 20 units
 - b. Lateral canthal area (crow's feet lines): up to 10 units on each side
 - c. Glabella (between eyebrows): up to 10 units
2. **Juvéderm Voluma XC**: up to 2 cc to the mid-face (cheeks)
 3. **Juvéderm Volbella XC**: up to 2 cc to the lips *and/or* perioral area, per participant preference and physician judgment

Study participants will be given the option to receive a touch-up at approximately 2 weeks after the initial procedure. At the optional 2 week touch-up visit, participants may elect to receive additional injections of any of the products, depending on their treatment preferences and the clinician's judgment.

REVERSAL AGENTS

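### A lip or perioral area first treated after the baseline form is given has no baseline score on its lip scale; giving both lip scales to everyone closes the gap

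*Combined protocol and SAP*

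**What the plan says.** Four parts of the protocol bear on this.

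- **Satisfaction Questionnaires, Baseline and Follow-up.** Both lists end with Appraisal of Lines: Lips and/or Satisfaction of Lips, given "depending on the area treated with filler". The baseline list is introduced with "The following surveys/questionnaires will be administered prior to the procedure". The scales for the other regions (between the eyebrows, forehead, crow's feet, cheeks) carry no such condition and go to everyone at both visits.
- **Dosage and Administration.** Volbella goes to the lips and/or the perioral area, "per participant preference and physician judgment". No time is given by which the choice must be fixed. At about 2 weeks, "participants may elect to receive additional injections of any of the products, depending on their treatment preferences and the clinician's judgment". Neither this section nor Follow-up limits those injections to areas already treated. Injection sites and treatment areas are recorded on the case report form.
- **Efficacy Assessments and Table 1.** Efficacy measures are taken only before treatment and at the 2-month visit. Table 1 schedules no satisfaction questionnaires at the touch-up visit, and its footnote lets screening and baseline fall on the same day.
- **Analysis Plan.** "Secondary outcome measures will also be analyzed using paired *t*-tests". The modified intent-to-treat population is not defined, and there is no rule for a missing baseline.

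**The concern.** The form is selected by something that has not yet happened. When the participant fills in the baseline questionnaires, no area has been treated, so the selection can only follow the area expected at that moment. If the expectation is wrong, or an area is added at 2 weeks, the 2-month form follows the area actually treated and the baseline form does not.

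A secondary objective is change on the FACE-Q Aesthetic Scales. A scale with a 2-month score and no baseline gives no change score, so the participant contributes nothing to that paired test. The gap cannot be repaired later: a baseline has to be taken before injection, and the schedule offers no questionnaire at touch-up, which would be the last chance to collect a score before the new area is treated.

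**Working it through.** The plan gives no figure to reproduce: the sample size of 20 is stated to rest on no power analysis.

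**Step 1. Who has a usable pair under the current wording?**

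| First procedure | Touch-up | Scale(s) at baseline | Scale(s) due at 2 months | Pair lost |
|---|---|---|---|---|
| Lips and perioral | any | both | both | none |
| Lips only | none, or lips again | Satisfaction | Satisfaction | none |
| Lips only | perioral added | Satisfaction | both | Lines |
| Perioral only | none, or perioral again | Lines | Lines | none |
| Perioral only | lips added | Lines | both | Satisfaction |
| Area differs from the one expected when the form was given | any | scale for the expected area | scale for the treated area | scale for the treated area |

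This assumes that the area rule at follow-up covers areas treated at either visit. If it covered only the first procedure, the added area would not be scored at 2 months at all, and the pair would still be missing.

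**Step 2. How many pairs?** Let *a* be the number treated in an area at the first procedure, with the matching baseline form, and *k* the number first treated there at touch-up. The scale is due from *a* + *k* participants but has *a* usable pairs. Each participant receives all three products at the first procedure, so everyone starts in at least one area. The *k* late additions therefore come from the 20 − *a* who started only in the other area.

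**Step 3. What does the loss cost?** For a two-sided paired t-test at 0.05 with n pairs, power for a standardised mean change d is approximately P(T > t(0.975, n−1)), where T is noncentral t with n−1 degrees of freedom and noncentrality d√n; the opposite tail is negligible. The detectable effect is the d that gives 80%. The 95% confidence interval half-width, in SDs of the change, is t(0.975, n−1)/√n. The protocol does not state sidedness; two-sided is assumed.

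The documents do not give *a* or *k*. Assume that 10 start in each single area and none in both, so *a* = 10, and vary *k*. Dropout is ignored.

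| *k* | Scale due from | Usable pairs as written | Detectable effect with all baselines | Detectable effect as written |
|---|---|---|---|---|
| 0 | 10 | 10 | 1.00 SD | 1.00 SD |
| 2 | 12 | 10 | 0.89 SD | 1.00 SD |
| 3 | 13 | 10 | 0.85 SD | 1.00 SD |
| 5 | 15 | 10 | 0.78 SD | 1.00 SD |
| 10 (extreme) | 20 | 10 | 0.66 SD | 1.00 SD |

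For *k* = 3, the half-width is 2.262/√10 = 0.72 SD as written, against 2.179/√13 = 0.60 SD with all baselines.

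At the other end, if all 20 are treated in both areas at the first procedure, then *a* = 20 and *k* = 0 for each scale, and nothing is lost.

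**Step 4. Should everyone be pooled once both scales are universal?** No. Suppose 10 of 20 are treated in an area with a true change of 0.8 SD, and the other 10 have zero mean change and the same SD. Pooling gives a mean of 0.5 × 0.8 = 0.40 and an SD of √(1 + 0.5 × 0.5 × 0.64) = 1.077, so d = 0.371. Power is 35% on all 20, against 62% on the 10 treated. The treated-area analysis is the one to keep.

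**The case against.** The strongest reply is that choosing the form by area is sensible. Asking about perioral lines only in people treated there is a defensible target, and the natural reading is that the area is agreed before the form is handed over. The wording is and/or, so anyone planned for both areas completes both scales. A touch-up in an area already treated loses no pair. The scales concerned are two of many secondary measures in a 20-person pilot with no power target.

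All of that stands, and it limits the size of the point. It does not remove the gap: even if the area is agreed beforehand, an area first treated at 2 weeks has no baseline.

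A reader might infer more than the documents support:

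- *Both lip scales will run on small subsets, and universal forms would restore 20 pairs.* The split between areas is not given, and either scale could be due from few participants or from all 20. A drop from 20 to 10 pairs because half are treated elsewhere comes from the treatment pattern. An analysis restricted to treated participants does not recover it.
- *Three late additions turn 10 pairs into 7.* Under an even split the additions come from the other group, so 13 are due and 10 are usable. Having 7 usable of 10 due would need 7 starting in that area and 13 in the other.
- *The lost pairs come from dissatisfied participants.* The Follow-up section says touch-up injections may be requested by the participant or recommended by the clinician. Why a new area would be added is not known, so a link to dissatisfaction is conjecture.
- *Untreated participants would serve as a check on expectation effects.* They are self-selected and receive Volbella in the adjacent area, as well as Botox and cheek filler. Their change does not isolate expectation.

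**Conclusion.** The gap follows from the text: the form is selected by area before treatment, the touch-up is open to new areas, no questionnaire is scheduled at that visit, and the test needs pairs. How often it will bite is unknown and could be zero. Under the illustrative assumption of 10 starting in each single area and 3 adding the other, one scale loses 3 of 13 pairs, and its detectable effect is 1.00 SD instead of 0.85 SD. Only the two lip scales are exposed. The primary scale, FACE-Q Satisfaction with Facial Appearance, is given to everyone at baseline and at 2 months and is unaffected. Severity is minor, but the change is worth making because it is cheap and a missed baseline cannot be recovered.

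**What to change.** - In both questionnaire lists, delete the condition on area treated and give both Appraisal of Lines: Lips and Satisfaction of Lips to all participants at baseline and at 2 months, as is already done for the other regional scales.
- In the Analysis Plan, state that each lip scale is analysed by paired t-test in participants treated in that area at either visit, identified from the treatment areas already recorded on the case report form, with n reported for each scale.
- State that any change in participants not treated in that area is descriptive only and is not pooled with the treated.

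The cost is at most one extra short questionnaire per participant per visit, and a few lines of text. Nothing about treatment or visit timing changes.
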